5.5.3 Supply, storage and tracking of study treatment

Study drugs must be received at the study site by a designated person, handled and stored safely and properly, and kept in a secured location to which only the Investigator and designated staff have access. Upon receipt, the study drugs should be stored according to the instructions specified on the drug labels.

Storage conditions must be adequately monitored and appropriate temperature/humidity logs maintained as Source data.

[figure not shown]
The Investigator must maintain an accurate record of the shipment and dispensing of study drug in a drug accountability ledger. Drug accountability will be noted by the Monitor during site visits and/or at the completion of the trial.

Patients will be asked to return all unused study drug and packaging at the end of the study or at the time of study drug discontinuation.

All drug supplies are to be used only for this protocol and not for any other purpose. Unless specifically instructed by Novartis, the Investigator must not destroy any drug labels, or any partly used or unused drug supply.

At the conclusion of the study, and, if allowed during the course of the study (e.g. an open label study or an un-blinded monitor), the Investigator will provide a copy of the drug accountability ledger to the Monitor.

Only after receiving a written authorization by Novartis, the Investigator will send all the unused and partly used drug supplies as well as the empty containers to the address provided at the time of authorization for destruction **or** have the unused and partly used drug supplies as well as the empty containers destroyed by the site's pharmacist, providing a drug destruction certificate.

5.5.3.1 Instructions for prescribing and taking study treatment

Patients will self-administer LCI699 p.o. b.i.d. in the morning and evening regardless of when they have eaten.

The investigator should promote compliance by instructing the patient to take the study drug exactly as prescribed and by stating that compliance is necessary for the patient's safety and the validity of the study. The patient should be instructed to contact the investigator if he/she is unable for any reason to take the study drug as prescribed.

The patients will also be instructed to bring back used and unused medication at selected time-points for drug accountability checking.

Patients must be instructed not to chew the medication, but to swallow it whole. All dosages prescribed and dispensed to the patient and all dose changes during the study must be recorded on the Dosage Administration Record eCRF.

5.5.4 Permitted dose adjustments and interruptions of study treatment

LCI699 dose will be titrated as outlined in [Section 3.1](#) or until normalization of UFC (below upper limit of normal, as per local lab levels). For patients who are unable to tolerate the protocol-specified dose scheme, dose adjustments are permitted. The following guidelines should be followed:

- If the patient has not reached normalization of UFC, but does not tolerate the current dose, administration of an intermediate dose between the current (untolerated) and preceding (tolerated) dose or repeated administration of the preceding, tolerated dose should be considered.
- If the patient has reached normalization of their UFC, but the current dose is no longer tolerated, an intermediate dose between the current dose and previous dose should be considered.
- If the patient had reached normalization of their UFC, but the current dose is no longer efficacious based on on-going UFC measurements, dose escalation should resume.
- If the patient has low serum cortisol or $UFC < LLN$, and the patient has signs/symptoms of adrenal insufficiency, a dose reduction of LCI699 should be considered.

These changes must be recorded on the Dosage Administration Record eCRF.

5.5.5 Dose modification and dose delay

For patients who do not tolerate the protocol-specified dosing schedule, dose adjustments are permitted in order to allow the patient to continue the study treatment. Instructions for monitoring liver function, and the criteria for withholding, re-initiating, reducing dose, or discontinuing study treatment are provided in [Table 5-1](#) below.

Table 5-1 Criteria for interruption and re-initiation of LCI699 for abnormal liver function

Isolated total Bilirubin elevation	
> ULN – 1.5 x ULN > 1.5 - 3.0 x ULN	Maintain dose level Interrupt study drug dose. Monitor liver function tests (LFTs) ^a , or more frequently if clinically indicated, until resolved to ≤ 1.5 x ULN: If resolved in ≤ 14 days, restart study drug and maintain dose level If resolved in > 14 days, then restart study drug and decrease by one dose level
> 3.0 - 10.0 x ULN*	Interrupt study drug. Monitor LFTs ^a weekly, or more frequently if clinically indicated, until resolved to ≤ 1.5 x ULN: If resolved in ≤ 14 days, then restart study drug and decrease by one dose level If resolved in > 14 days, then discontinue patient from study drug treatment. The patient should be monitored weekly (including LFTs ^a), or more frequently if clinically indicated, until total bilirubin has resolved to baseline or stabilized over 4 weeks.
> 10.0 x ULN*	Discontinue patient from study drug treatment The patient should be monitored weekly (including LFTs ^a), or more frequently if clinically indicated, until total bilirubin has resolved to baseline or stabilized over 4 weeks.
Isolated AST or ALT elevation	
> ULN - 3.0 x ULN > 3.0 - 5.0 x ULN	Maintain dose level Maintain dose level. Repeat LFTs ^a as soon as possible, preferably within 48-72 hours from awareness of the abnormal results; if abnormal lab values are confirmed upon the repeat test, then monitor LFTs ^a weekly, or more frequently if clinically indicated, until resolved to ≤ 3.0 x ULN
> 5.0 - 10.0 x ULN	Interrupt study drug. Repeat LFTs ^a as soon as possible, preferably within 48-72 hours from awareness of the abnormal results; monitor LFTs ^a weekly or more frequently if clinically indicated, until resolved to ≤ 3.0 x ULN. Then: If resolved in ≤ 14 days, restart study drug and maintain dose level If resolved in > 14 days, restart study drug and decrease dose by one level If not resolved after 4 weeks, discontinue patient from study drug.
>10.0 – 20.0 x ULN	Interrupt study drug. Repeat LFTs ^a as soon as possible, preferably within 48-72 hours from awareness of the abnormal results; monitor LFTs ^a weekly, or more frequently if clinically indicated, until resolved to ≤ 3.0 x ULN Then restart study drug and decrease by one dose level.
> 20.0 x ULN	Discontinue patient from study drug treatment Repeat LFTs ^a as soon as possible, preferably within 48-72 hours from awareness of the abnormal results; monitor LFTs ^a weekly, or more frequently if clinically indicated, until returned to baseline or stabilized over 4 weeks.

Combined^{b, d} elevations of AST or ALT and total bilirubin	

For patients with normal baseline ALT and AST and total bilirubin value
 
AST or ALT >3.0 x ULN combined with total bilirubin >2.0 x ULN without evidence of cholestasis^c
 
OR
 
For patients with elevated baseline AST or ALT or total bilirubin value [AST or ALT > 2x baseline AND > 3.0 x ULN] OR [AST or ALT > 8.0 x ULN], combined with [total bilirubin > 2 x baseline AND > 2.0 x ULN]
	
Permanently discontinue patient from study drug treatment.
 
Repeat as soon as possible, preferably within 48 hours from awareness of the abnormal results, then with weekly monitoring of LFTs^a, or more frequently if clinically indicated, until AST, ALT, or bilirubin have resolved to baseline or stabilization over 4 weeks.
 
Refer to Section 5.5.6 for additional follow-up evaluations as applicable.


All dose modifications should be based on the worst preceding toxicity.
 
a. Core LFTs consist of ALT, AST, GGT, total bilirubin (fractionated [direct and indirect], if total bilirubin > 2.0 x ULN), and alkaline phosphatase (ALP) (fractionated [quantification of isoforms], if alkaline phosphatase > 2.0 x ULN.)
 
b. "Combined" defined as: total bilirubin increase to the defined threshold concurrently with ALT/AST increase to the defined threshold
 
If combined elevations of AST or ALT and total bilirubin do not meet the defined thresholds, please follow the instructions for isolated elevation of total bilirubin and isolated elevation of AST/ALT, and take a conservative action based on the degree of the elevations (e.g. discontinue study drug in the situation when interrupt study drug is required for one parameter and discontinue study drug is required for another parameter). After all elevations resolve to the defined thresholds that allow treatment re-initiation, re-start the treatment either at the same dose or at one dose lower if meeting a criterion for dose reduction.
 
c. "Cholestasis" defined as: ALP elevation (>2 x ULN and R value (ALT/ALP in x ULN) < 2) in patients without bone metastasis, or elevation of ALP liver fraction in patients with bone metastasis
 
Note: (The R value is calculated by dividing the ALT by the ALP, using multiples of the ULN for both values. It denotes whether the relative pattern of ALT and/or ALP elevation is due to cholestatic (R ≤ 2), hepatocellular (R ≥ 5), or mixed (R > 2 and < 5) liver injury. See Section 5.5.6)
 
* Note: If total bilirubin > 3.0 x ULN is due to the indirect (non-conjugated) component only, and hemolysis as the etiology has been ruled out as per institutional guidelines (e.g., review of peripheral blood smear and haptoglobin determination), then ↓ 1 dose level and continue treatment at the discretion of the investigator.
	

5.5.6 Follow up on potential drug-induced liver injury (DILI) cases

Patients with transaminase increase combined with TBIL increase may be indicative of potential DILI, and should be considered as clinically important events.

The threshold for potential DILI may depend on the patient's baseline AST/ALT and TBIL value; patients meeting any of the following criteria will require further follow-up as outlined below:

- For patients with normal ALT and AST and TBIL value at baseline: AST or ALT > 3.0 x ULN combined with TBIL > 2.0 x ULN
- For patients with elevated AST or ALT or TBIL value at baseline: [AST or ALT > 2 x baseline AND > 3.0 x ULN] OR [AST or ALT > 8.0 x ULN], combined with [TBIL > 2 x baseline AND > 2.0 x ULN]

Medical review needs to ensure that liver test elevations are not caused by cholestasis, defined as ALP elevation > 2.0 x ULN with R value < 2.

Note: (The R value is calculated by dividing the ALT by the ALP, using multiples of the ULN for both values. It denotes whether the relative pattern of ALT and/or ALP elevation is due to cholestatic ($R \leq 2$), hepatocellular ($R \geq 5$), or mixed ($R > 2$ and < 5) liver injury).

In the absence of cholestasis, these patients should be immediately discontinued from study drug treatment, and repeat LFT testing as soon as possible, preferably within 48 hours from the awareness of the abnormal results. The evaluation should include laboratory tests, detailed history, physical assessment and the possibility of liver lesions, obstructions/compressions, etc.

- Laboratory tests should include ALT, AST, albumin, creatine kinase, total bilirubin, direct and indirect bilirubin, GGT, prothrombin time (PT)/ international normalized ratio (INR) and alkaline phosphatase.
- A detailed history, including relevant information, such as review of ethanol, concomitant medications, herbal remedies, supplement consumption, history of any pre-existing liver conditions or risk factors, should be collected.
- Further testing for acute hepatitis A, B, C or E infection and liver imaging (e.g. biliary tract) may be warranted.
- Additional testing for other hepatotropic viral infection (CMV, EBV or HSV), autoimmune hepatitis or liver biopsy may be considered as clinically indicated or after consultation with specialist/hepatologist.

All cases confirmed on repeat testing meeting the laboratory criteria defined above, with no other alternative cause for LFT abnormalities identified, should be considered as “medically significant”, thus, met the definition of SAE ([Section 7.2](#)) and reported as SAE using the term “potential drug-induced liver injury”. All events should be followed up with the outcome clearly documented.

5.5.7 Rescue medication

As this is the first study to evaluate LCI699 for Cushing’s disease there are no established rescue medications. If patients are not responding to, or not tolerating LCI699, they should be withdrawn from the study and other accepted therapies (surgical resection or other medications) should be initiated.

5.5.8 Concomitant treatment

Stable doses of concomitant medications (except those for hypercortisolism) are allowed during the study. All pre-existing concomitant medications should be recorded at study start. The investigator should instruct the patient to notify the study site about any new medications he/she takes after the start of the study. All medications and significant non-drug therapies (including physical therapy and blood transfusions) administered after the patient signs the informed consent must be listed on the Concomitant medications/Significant non-drug therapies after start of study (e)CRF.

Should a patient have an incidental and limited need for a medication to be taken within the restricted pre-dose timeframe (e.g. ibuprofen for a headache, antibiotic prophylaxis prior to dental surgery etc.), the sponsor should be advised, as administration of any concomitant medication may require the patient to be replaced. Decisions regarding replacements will be

discussed with the sponsor on a case-by-case basis. Administration of paracetamol, (acetaminophen) is acceptable, but must be documented.

All prescription medications and over-the-counter drugs taken within the timeframe defined in the entry criteria prior to the start of the study and during the study, must be recorded on the Concomitant Medications/ Non-Drug Therapies page of the e(CRF). Medication entries should be specific to trade name, the single dose and unit, the frequency and route of administration, the start and discontinuation date and the reason for therapy.

5.5.9 Prohibited treatment

Use of other drug treatments for Cushing's disease is prohibited during this study. Patients on drugs for ailments other than Cushing's disease will be checked by the Investigator against the list of known substrates of CYP1A2, CYP2D6 and CYP2E1 (see detailed list in [Appendix 3](#)). For any concomitant medications on this list, an alternate drug may be prescribed, dose adjusted of the concomitant medication as per the product label or dose limitation of LCI699 should be considered by the Investigator.

Preclinical data and preliminary clinical data indicate that there is a potential risk of QTc prolongation in humans (see Amendment 5 Rationale). Therefore, the use of medications with a "Known risk to cause TdP" and drugs with a "Possible risk to cause TdP" concomitantly with LCI699 is prohibited.

If a patient requires a long-term medication from the two categories mentioned above, and there is no adequate alternative medication available, then they should be discontinued from the study.

However, if a patient requires such a drug for short-term therapy, e.g., antibiotics for active infection, then the LCI699 may be interrupted temporarily while this drug is administered after a thorough risk-benefit assessment. This does not require the patient to discontinue from the study. Washout periods for LCI699 and the short-term prohibited drug in many cases may not be possible; this is acceptable if the benefit of the drug outweighs the risk of withholding LCI699 therapy in the investigator's judgment. In such cases, a discussion with the Novartis Medical Monitor is recommended.

Investigators are advised to refer to [Appendix 6](#) and utilize the www.crediblemeds.org website when considering the addition of a new concomitant medication, with risks of TdP, as the lists are periodically updated.

If necessary, a discussion can be held with the Novartis Medical Monitor when considering the use of medications with a "known risk to cause TdP" and with a "possible risk to cause TdP".

In addition, the following drugs are prohibited: spironolactone, eplerenone, and glucocorticoids (e.g., prednisone, dexamethasone). Please note the following exceptions to these prohibitions: eplerenone may be used if necessary in acute post-myocardial infarction management, and in the event of refractory hypokalemia in patients with hypertension or edema; glucocorticoids may be used as required for the short-term treatment of adrenal insufficiency.

If glucocorticoids are used in stress doses, or as replacement therapy, for > 4 weeks, then the investigator should consider temporary interruption of LCI699, weaning and discontinuation of glucocorticoid therapy, or early discontinuation from the study.

5.5.10 Concomitant medication to be use with caution

Emerging preclinical data suggest that CYP3A4/5 and CYP2D6 may be involved in LCI699 metabolism; while relative contribution of these enzymes to LCI699 metabolism *in vivo* is not yet elucidated, risk exists for drug-drug interaction with medications that are strong CYP3A4/5 and CYP2D6 inhibitors and inducers ([Appendix 7](#)). Therefore concomitant medications that are known strong inhibitors or inducers of CYP3A4/5 and CYP2D6 are to be used with caution with LCI699.

5.5.11 Discontinuation of study treatment

Patients may voluntarily discontinue from the study treatment for any reason at any time. If a patient decides to discontinue from the study treatment, the investigator should make a reasonable effort (e.g. telephone, email, letter) to determine the primary reason for this decision and record this information in the patient's chart and on the appropriate CRF pages. They may be considered withdrawn if they state an intention to withdraw, fail to return for visits, or become lost to follow-up for any other reason.

The investigator should discontinue study treatment for a given patient if he/she believes that continuation would be detrimental to the patient's well-being.

Study treatment must be discontinued under the following circumstances and according to Investigator discretion:

- Withdrawal of informed consent.
- Emergence of the following adverse events (compound specific):
 - hypertension defined as office mean sitting systolic BP > 180 mmHg or mean sitting diastolic BP > 110 mmHg (confirmed and persistent*).
- Any of the following laboratory abnormalities:
 - hyperkalemia (serum potassium > 5.5 mmol/L; confirmed and persistent*).
 - hypokalemia (serum potassium < 3.5 mmol/L; confirmed and persistent*).
 - hyponatremia (serum sodium < 130 mmol/L; confirmed and persistent*).
- QTcF > 500 msec, if confirmed by a cardiologist (see [Section 6.6.5](#)).
- QTcF > 480 msec, if the investigator determines it is no longer safe for the patient to continue in the study, based on ECGs, cardiac examination, and recommendation from a cardiologist (see [Section 6.6.5](#)).
- Pregnancy.
- Use of any other therapy for Cushing's disease.
- Any other protocol deviation that results in a significant risk to the patient's safety.

* Persistent is defined as unresolved with LCI699 dose or other concomitant medication changes

Patients who discontinue study treatment should NOT be considered withdrawn from the study. They should return for the assessments indicated in [Section 6](#). If they fail to return to return for these assessments for unknown reasons, reasonable effort (e.g. telephone, email, letter) should be made to contact them as specified in [Section 5.5.13](#).

5.5.12 Withdrawal of Consent

Subjects may voluntarily withdraw consent to participate in the study for any reason at any time. Withdrawal of consent occurs only when a subject:

- Does not want to participate in the study anymore, and
- Does not allow further collection of personal data

In this situation, the investigator should make a reasonable effort (e.g. telephone, e-mail, letter) to understand the primary reason for the subject's decision to withdraw his/her consent and record this information.

Study treatment must be discontinued and no further assessments conducted, and the data that would have been collected at subsequent visits will be considered missing.

Further attempts to contact the subject are not allowed unless safety findings require communicating or follow-up.

All efforts should be made to complete the assessments prior to study withdrawal. A final evaluation at the time of the subject's study withdrawal should be made as detailed in the assessment table.

Novartis will continue to keep and use collected study information (including any data resulting from the analysis of a subject's samples until their time of withdrawal) according to applicable law.

For US and Japan: All biological samples not yet analyzed at the time of withdrawal may still be used for further testing/analysis in accordance with the terms of this protocol and of the informed consent form.

[figure not shown]
For EU and RoW: All biological samples not yet analyzed at the time of withdrawal will no longer be used, unless permitted by applicable law. They will be stored according to applicable legal requirements.

5.5.13 Lost to follow-up

For patients whose status is unclear because they fail to appear for study visits without stating an intention to withdraw consent, the investigator should show "due diligence" by contacting the patient, family, or family physician as agreed in the informed consent, and by documenting in the source documents steps taken to contact the patient, e.g. dates of telephone calls, registered letters, etc. A patient should not be considered lost to follow up until due diligence has been completed. Patients lost to follow up should be recorded as such on the appropriate Disposition CRF.

5.5.14 Emergency unblinding of treatment assignment

Not applicable as study is open-label.

5.5.15 Study completion and post-study treatment

Patient treatment in Long Term Extension-2 will end at each site within 4 months after a separate roll-over study is opened at their site, or by 31 December 2019 (whichever occurs earlier). The roll-over study will provide an opportunity of continued treatment for patients who are still ongoing at that time and who are clinically benefitting from LCI699.

Sites with the separate roll-over study option available, should arrange an End of Trial (EOT) visit within 4 months of the roll-over study opening at their site (i.e. earlier than the 6 month interval visits in Long Term Extension-2), to allow their patients to continue their LCI699 dose on this new study.

For sites where a separate roll-over study is not option, the patient may be offered a local alternative treatment option and must complete their Long-Term Extension-2 EOS visit by 31 December 2019.

The investigator must provide follow-up medical care for all patients who are prematurely withdrawn from the study, or must refer them for appropriate ongoing care.

5.5.16 Early study termination

The study can be terminated at any time for any reason by Novartis. Should this be necessary, the patient should be seen as soon as possible and treated as described in [Section 6](#) for a discontinued patient. The investigator may be informed of additional procedures to be followed in order to ensure that adequate consideration is given to the protection of the patient's interests. The investigator will be responsible for informing IRBs and/or ECs of the early termination of the trial.

The study will be stopped if any of the following criteria are met: and no further patients enrolled pending a full safety review:

- At least 3 patients manifest a similar unexpected/off-target AE which is > CTCAE (v4) grade 2 ([Appendix 5](#)), suspected to be related to study drug and that does not resolve with drug reduction
- At least 3 patients are withdrawn from the study for adverse events as described under the individual withdrawal rules below

6 Visit schedule and assessments

The full [Assessment schedules](#) is presented before [Section 1](#).

Patients should be seen for all visits on the designated day with a visit window of ± 2 days. Due to the circadian rhythm nature of steroid levels (including cortisol), patients are advised to come to the site on a fixed time window (e.g. ± 2 hours) for each of the visits and best efforts should be made to keep consistent throughout the study.

Patients who discontinue study treatment before completing the study, and those who discontinue from the study for any reason, should be scheduled for a visit as soon as possible, at which time all of the assessments listed for the End of Treatment visit. In addition, an End of Study visit will be performed 28 days after the last dose administration. Every effort will be made to take the pharmacokinetic sample at the protocol specified time.

Patients entering the roll-over protocol will complete an EOT visit. Their EOT visit should be arranged within 4 months of the roll-over study opening at their site. For these patients the EOS visit is not applicable, as treatment on LCI699 will not be interrupted.

Patients not continuing into the roll-over protocol will complete an EOT visit upon stopping treatment, and an EOS visit 28 days after the last dose administration, must be completed by 31 December 2019. Any repeat assessments associated with this visit should be documented and followed-up appropriately by the Investigator.

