Stage	A major subdivision of the study timeline; begins and ends with major study milestones such as enrollment, randomization, completion of treatment, etc.
Stop study participation	Point/time at which the patient came in for a final evaluation visit or when study drug was discontinued whichever is later.
Study drug	Any drug administered to the patient as part of the required study procedures; includes investigational drug and any control drugs.
Study drug discontinuation	Point/time when patient permanently stops taking study drug for any reason;
Subject	An individual who has consented to participate in this study. The term Subject may be used to describe either a healthy volunteer or a patient.
Variable	Information used in the data analysis; derived directly or indirectly from data collected using specified assessments at specified timepoints.
Withdrawal of Consent	Withdrawal of consent occurs only when a patient does not want to participate in the study any longer, and does not want any further visits or assessments, and does not want any further study related contact

Amendment 9 (03-May-2018)

Amendment Rationale

Of the 19 patients initially enrolled under Amendment 4, 10 patients are still ongoing as of 03 May 2018.

The purpose of this amendment is to extend the study end date from 31 December 2018 to 31 December 2019 to allow continued access to the study drug for those patients benefitting from the treatment until a separate long-term safety follow-up study (roll-over study) is set up at participating sites.

Additional updates were made to the Protocol glossary and withdrawal of informed consent section to align with the new Personal Data and Withdrawal of Consent language requirement.

Due to the extension of the study duration, this amendment is classified as substantial.

Changes to the protocol and the ICF

[figure not shown]
- Protocol synopsis and Sections 3.1, 5.5.15, and 6: Long Term Extension-2 end day changed from 31 December 2018 to 31 December 2019
- Glossary: Updated Personal Data and Withdrawal of Consent language
- Section 5.5.12 Updated Withdrawal of Consent language
- Updates to the ICF include updating the study end date from 31 December 2018 to 31 December 2019 throughout the document and the implementation of General Data Protection Regulation (“GDPR”) language for sites in the European Union.

IRB/IEC

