Some patients who enter this study may wash out current drug therapies in order to participate in this trial. It is to be expected that patients willing to consider washout of current therapies are those who are not responding to or tolerating their current therapies, and for whom the risk of a relatively short washout may be considered acceptable to test whether another therapy works better. There is a theoretical risk that if current effective therapy would be withdrawn, that cortisol levels would increase, and that patients would not respond well to LCI699. However, preliminary data from this PoC study indicate that all patients analyzed responded to LCI699. There is a risk that some patients may lose UFC control over time (“therapeutic escape”) while participating in the longer treatment evaluation. If a patient is not responding

to, or not tolerating an effective dose of, LCI699, they can be withdrawn from the study and resume their prior therapy.

Potential impact of delaying therapy

Some patients who enter this study may have a new diagnosis of Cushing's disease. The standard of care therapy for Cushing's disease is surgical resection of the ACTH producing tumor.

Entry into this study may delay the time to the provision of standard effective therapy. If LCI699 is effective, initiation of medical therapy to reduce excess cortisol may improve patient symptoms and improve medical co-morbidities which can improve their ability to tolerate the surgery. If LCI699 is not effective, the patient may experience extra weeks of excess cortisol exposure. If a patient is not responding to, or not tolerating an effective dose of, LCI699 they can be withdrawn from the study and undergo surgical resection.

The standard of care therapy for Cushing's disease is surgical resection of the ACTH producing tumor. Cushing's disease patients enrolled under [Amendment 4](#) should have either failed standard therapy (including surgery) or can be de novo patients for whom surgery is not an option.

Preliminary data from this PoC study demonstrated that LCI699 is an effective medical therapy to reduce hypercortisolism. If a patient is not responding to, or not tolerating an effective dose of, LCI699 they can be withdrawn from the study ([Section 5.5.9](#)).

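### The second study-stopping criterion (Protocol 5.5.16) counts withdrawals from the study, but the individual safety rules mainly stop study drug, and 5.5.11 says that is not withdrawal

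*Protocol*

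**What the plan says.** Protocol 5.5.16 gives two criteria, either of which stops the study and halts enrolment until a full safety review. The first needs at least 3 patients with a similar unexpected or off-target event above CTCAE grade 2 that is suspected to be drug-related and persists despite dose reduction. The second is: "At least 3 patients are withdrawn from the study for adverse events as described under the individual withdrawal rules below". Section 5.5.16 ends there and Section 6, the visit schedule, begins.

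The rules for the individual patient are elsewhere:

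- 5.5.11 lists blood pressure, potassium, sodium and QTcF limits, among others, at which study treatment must be discontinued.
- Table 5-1 in 5.5.5 gives the liver limits for interrupting or permanently stopping study drug.
- 6.6.5 gives the QTcF algorithm.

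On the status of a patient who stops drug, 5.5.11 says: "Patients who discontinue study treatment should NOT be considered withdrawn from the study". It then asks that they return for the Section 6 assessments. Section 5.5.7 says: "If patients are not responding to, or not tolerating LCI699, they should be withdrawn from the study". Section 3.5 says three times that patients who do not respond to or tolerate the drug may leave, for example that "they can be withdrawn from the study and resume their prior therapy" or that "they can be withdrawn from the study and undergo surgical resection". Section 9.5.2 describes an exit for adverse events as discontinuing the study.

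**The concern.** A count-based safety trigger needs a defined event to count. This one borrows its event from rules that are not where it says they are. The rules that do exist mostly produce a different event: study drug stops and the patient stays for follow-up. If 5.5.11 governs, the trigger is largely emptied, because the patients it was presumably meant to catch are by definition not withdrawn. If 5.5.7 governs, they count.

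What is at stake is whether a mandatory safety review happens. The first criterion is not a full substitute. Three patients stopped for different events, or for events already expected with this drug, would meet only the second. The practical effect now falls on continued treatment rather than enrolment: the Amendment 9 rationale reports 10 of the 19 Amendment 4 patients still on study.

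**Working it through.** The plan attaches no error rate or probability to this rule, so there is no figure to reproduce. The check is of the text, followed by a worked count.

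**Step 1. Is there anything below 5.5.16 that fits?** Section 6.6.5 has QTcF rules, and 6.6.7 has a stop for pregnancy. Neither is a set of withdrawal rules for adverse events. The main list, 5.5.11, and Table 5-1 are above. The pointer is wrong about direction, and also about the kind of rule.

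**Step 2. What do the individual rules do?** Mostly they end or interrupt study drug. There is an exception in wording: 5.5.11 ends treatment for QTcF above 480 msec "if the investigator determines it is no longer safe for the patient to continue in the study", and 6.6.5 likewise speaks of continuing in the trial.

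**Step 3. Does stopping drug make a patient withdrawn?**

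| Place | What it implies for the count |
|---|---|
| 5.5.11 | Stopping treatment is not withdrawal. The grounds it gives for being considered withdrawn are stated intention, missed visits or loss to follow-up. |
| 5.5.7 | Patients who do not tolerate the drug should be withdrawn, so they count. |
| 9.5.2 (and SAP 7.3.2.4) | An adverse-event exit is called discontinuing the study, which leans toward counting. |
| Glossary, stop study participation | The later of the final evaluation visit and drug discontinuation. It dates the end of participation and does not define withdrawal. |
| Section 6 | Names treatment discontinuers and study discontinuers separately, but gives both an end-of-treatment visit and an end-of-study visit 28 days after last dose. |
| 3.5 | Patients can be withdrawn. This is a permission, compatible with either reading. |

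The glossary defines study drug discontinuation ("Point/time when patient permanently stops taking study drug for any reason") and withdrawal of consent. It has no entry for withdrawal from the study.

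**Step 4. Worked count (assumed, not observed).** Three patients permanently stop study drug for adverse events under 5.5.11, Table 5-1 or 6.6.5 and return for follow-up.

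- Under 5.5.11 taken literally: 0 + 0 + 0 = 0, below 3, and the study continues.
- Under 5.5.7: 1 + 1 + 1 = 3, and the study stops.

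A patient who leaves the study outright because of such an event counts either way.

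**Step 5. Is a threshold of 3 within reach?** Take N = 19 (Amendment 9 rationale). Let p be an assumed chance that a patient permanently stops drug for an adverse event under the listed rules, the same for all and independent. If such stops count,

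P(at least 3) = 1 − Σ C(19, k) p^k (1 − p)^(19 − k), summed over k = 0, 1, 2.

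At p = 10%: 1 − (0.135 + 0.285 + 0.285) = 0.295.

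| Assumed p | P(at least 3 of 19) if stops count | From these stops alone if they do not |
|---|---|---|
| 5% | 6.7% | 0 |
| 10% | 29.5% | 0 |
| 20% | 76.3% | 0 |

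The documents give no value for p, so the table shows only that the choice of reading can matter at this sample size.

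**Step 6. Cross-references.** Section 3.5 (twice) and 6.6.5 (twice) cite 5.5.9 for the stop criteria. Section 5.5.9 is now the section on prohibited treatment. That makes 2 + 2 = 4 outdated references.

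**The case against.** The best reply is that any sensible safety reader would take the pointer to mean 5.5.11 and would count patients stopped under it. The 5.5.11 sentence is followed at once by the request to return for assessments, so its evident purpose is to protect follow-up rather than to define a numerator. The glossary entry on stopping participation, the shared visit schedule in Section 6 and the wording of 9.5.2 all lean the same way. A reading that nearly empties a safety rule is unlikely to be the intended one.

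Most of that stands as evidence of intent. It does not settle the text. Redirecting the pointer to 5.5.11 leads the reader to the very sentence that says these patients are not withdrawn, and none of the supporting places defines withdrawal from the study.

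Two stronger readings are tempting and should be resisted. A reader might infer that the protocol has no stopping rules for the individual patient. It has them, in three sections; only the pointer and the counted event are at fault. A reader might also set the three statements in 3.5 against 5.5.11 as direct contradictions. They say patients can be withdrawn, in risk-benefit narrative that also covers non-response, and a permission does not conflict with a rule that stopping drug is not in itself withdrawal. The real tension is with 5.5.7.

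**Conclusion.** The criterion is wrong as written. It counts an event that the individual safety rules mostly do not produce, and the protocol gives conflicting signals on whether the event they do produce should count. In the worked case the difference is 0 against 3 on a threshold of 3.

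The consequence is limited. The first criterion is unaffected, the sponsor may terminate the study at any time, and no estimate, interval or analysis set depends on this rule. A reader might infer that a trigger was missed. The documents do not support that: they give no study-wide count of drug stops for adverse events, and the reasons why 9 of the 19 Amendment 4 patients (19 − 10) were no longer ongoing at Amendment 9 are not broken down. The conclusion rests on the current protocol text alone; the probabilities above are illustrations and carry no weight in it.

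**What to change.** Reword the second criterion in 5.5.16 to: *At least 3 patients permanently discontinue study drug for an adverse event under the individual discontinuation rules in Sections 5.5.5 (Table 5-1), 5.5.11 or 6.6.5, whether or not they remain in the study for follow-up.*

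This uses an event the glossary already defines and keeps both the threshold of 3 and the clinical limits. It no longer depends on what withdrawn means, so it works even if 5.5.7 is left alone. Section 7.1 already says when a laboratory abnormality is an adverse event, and 6.6.5 already has notable ECG abnormalities recorded as adverse events.

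The wording deliberately stays with the listed rules. Counting every drug stop for an adverse event, such as one for nausea or fatigue outside those rules, would widen the trigger. Whether to do so is the sponsor's decision and is not part of this change.

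As housekeeping, change the four references to 5.5.9 (two in 3.5, two in 6.6.5) to 5.5.11.

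The cost is one sentence and four cross-references, with no change to visits, data collection or analysis. Because the sentence settles what a safety trigger counts, the sponsor's safety function should agree it.
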